#### Body Temperature and Respiration Rate

Body temperature (°C) and respiration rate (breaths/minute) will be obtained in the sitting position following at least 5 minutes of rest.

### 11.14. ECG (12-lead)

Single 12-lead ECGs will be performed following a period of at least 10 minutes of rest in the supine position. ECGs will be collected according to the SOA (Table 3). During Visit 2 ECG will be collected prior to dosing and ~8 hours post-dose.

#### 11.14.1. ECG Procedures

All ECGs should be performed according to the SOA (Table 3) with the following guidelines:

- ECG technicians should be thoroughly trained in the administration of a 12-Lead ECG, the institution's specific protocols and procedures for ECG tests, and the requirements of the study protocol.
- The same make and model of ECG machine with the same style of leads should be used for all patients. Such equipment should be recently serviced and calibrated. Machine calibration records and performance data should be maintained on file.
- Patients should be in a supine position and have rested for 10 minutes.

#### 11.14.2. Reading ECGs

- Site Monitoring: Sites should read ECGs for study monitoring and eCRFs per their usual procedures.
- Central Reading: The Sponsor may elect, if needed for regulatory reasons, to collect ECGs for Central Reading. If so, the intention will be that a single Central Reader will read all ECGs. Therefore, all ECGs must be available and stored for this purpose. When sent for Central Reading, the ECGs must be prepared to be read in a blinded fashion. Central Readers of ECGs should be blinded to time, treatment, and patient identifier.

### 11.15. Pregnancy Test

### Contraception

[figure not shown]
Females must not be pregnant and must have a negative serum pregnancy test result at the Screening Visit and negative urine pregnancy test on Day 1, with results known prior to initiating dosing; pregnancy testing will be monitored during the study.

For females able to bear children, including pre-pubertal females if relevant, a highly reliable form of contraception must be used/practiced throughout the study and for 90 days following the study. Highly reliable acceptable forms of contraception include hormonal (i.e., oral, implantable, or injectable) AND single-barrier method (i.e., condom), or an Intrauterine Device (IUD) AND single-barrier method (i.e., condom) or vasectomized partner. True abstinence is acceptable only if it is the preferred and usual lifestyle of the patient.

Females of non-childbearing potential, defined as surgically sterile (status post hysterectomy, bilateral oophorectomy, or bilateral tubal ligation), post-menopausal for at least 12 months, or delayed pubertal development and failure to have achieved menarche, do not require contraception during the study. Younger female patients who are not sexually mature will be assessed for Tanner Staging and advised accordingly. Females who begin the study having failed to reach Tanner Stage 5 or achieve menarche, but do so during the study, will be counseled on pregnancy and contraception, and will immediately be treated as a female of child-bearing potential for the remainder of the study, with the required pregnancy tests at all visits.

It is not known if this treatment will affect spermatogenesis. Therefore, males with female partners of childbearing potential must agree to use contraception: (A) use a double barrier method [i.e., condom AND diaphragm with spermicide during intercourse]), (B) had a vasectomy, or (C) abstain from sexual intercourse. True abstinence is acceptable only if it is the preferred and usual lifestyle of the patient. Male patients must not donate sperm for 90 days following participation in the study.

[figure not shown]

[figure not shown]

[figure not shown]
For all patients, the daily hunger questionnaire will be completed prior to the morning meal (fasted) and prior to dosing each day in the morning.

The Global Hunger Questions and Daily Hunger Questionnaire are described in Appendix G. The Global Hunger Questions will be completed during specified study visits at the clinic and the Daily Hunger Questionnaire will be recorded each day directly into an electronic data capture device (paper version can be used if needed).

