#### **Treatment Period**

Eligible patients will return to the clinic within 8-2 weeks of completing the Screening Visit for the Baseline Visit (Visit 2) and first dose of setmelanotide.

Dose levels for all patients will escalate to a final dose of 3.0 mg/day during an initial dose-titration phase, but the starting dose will depend on patient age. Patients 6 up to 16 years old will initially be dosed at 1.0 mg/day for 2 weeks, beginning at the Baseline Visit on Study Day 1. Starting on Day 15, the dose will escalate to 2.0 mg/day and remain at that level for 2 weeks, until the patient returns to clinic for Visit 3 on Day 29. At Visit 3, the dose will be escalated to 3.0 mg/day; the patient will continue dosing at 3.0 mg/day for 12 weeks.

Patients ≥16 years old will initiate dosing at 2.0 mg/day at the Baseline Visit, and continue dosing at that level for 2 weeks. The dose will be escalated to 3.0 mg/day beginning on Study Day 15, and the patient will continue that dose for 14 weeks.

Study site staff will call all patients at their homes after the first 2 weeks of treatment to ensure the escalation occurred as planned and collect any AEs.

Patients will continue dosing at 3.0 mg/day, and return to the clinic every four weeks (Visits 3-5) to complete the assessments in Table 3. After 16 weeks in the study, patients will return to the clinic for Visit 6. At Visit 6, the patient will receive the last setmelanotide injection. Participation in the study will then conclude in one of the following two ways:

• Complete Visit 6 and enroll in a separate extension study, Rhythm Study RM-493-022. If RM-493-022 is not yet open at the clinic site, the patient will continue daily setmelanotide injections and other activities per the current study, as presented in the SOA (Table 3). The patient will return to the clinic for Bridging Visits every 12 weeks for up to one year, until the extension study opens at the site. Additional clinic visits may be scheduled at the discretion of the PI.

[figure not shown]
• Decide not to participate in the extension study and proceed to the final study visit (Visit 7) in 4 weeks.

Patients on study per a previous amendment should transition to dose escalation as outlined in this protocol:

- Patients who are in the dose titration phase and are not currently at a dose of 3.0 mg/day will be assessed by the Primary Investigator and the Sponsor, to determine if an increase in the dose to 3.0 mg/day is appropriate.

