## 10. SCHEDULE OF ASSESSMENTS

The Schedule of Assessments (SOA) is presented in Table 3.

**Table 3:** Schedule of Assessments

Study Period/Procedure	Screening	Study Treatment			EOS Visit	Bridging Visit(s) 31				
Clinic Visit Number	V1	V2	-	V3 	V4	V5	V6 30	V7	+ up to 12 weeks from V6	Treatment Discontinuation
Start of Week X	-8 to -2	0	2	4	8	12	16	20	(up to one year	Visit
Study Day (± 3 days)	-56 to -14	1	15	29	57	85	113	141	from V6)	
Sponsor review of patient genetics/Genetic Testing 	X									
Informed consent/Assent 33	X									
Inclusion/Exclusion review	X	X								
Medical history review	X									
Physical examination 	X	X		X	X	X	X	X	X	X
Comprehensive skin exam 	X						X			X
Fitzpatrick classification scale	X						X	X		X
Hepatic imaging 	X									
Weight 	X	X		X	X	X	X	X	X	X
Waist circumference 	X	X		X	X	X	X	X	X	X
Height 	X			X	X	X	X	X	X	X
Vitals 	X	X		X	X	X	X	X	X	X
ECG (12-lead) 9	X	X 		X			X		X	X
Pregnancy test 	X	X 32		X	$X^{32}$	$X^{32}$	$X^{32}$		$X^{32}$	$X^{32}$
Daily hunger questionnaires 11	X			•	Daily	32	•			$X^{32}$
Global hunger assessment 12		$X^{32}$		X 	$X^{32}$	$X^{32}$	X 	X	$X^{32}$	$X^{32}$

Table 3: Schedule of Assessments (Continued)

Study Period/Procedure	Screening			Study T	reatme	nt		EOS Visit	Bridging Visit(s) 31		
Clinic Visit Number	V1	V2	-	V3 	V4	V5	V6 30	V 7	+ up to 12 weeks from V6	Treatment Discontinuation	
Start of Week X	-8 to -2	0	2	4	8	12	16	20	(up to one year from V6)	Visit	
Study Day (± 3 days)	56 to 14	1	15	29	57	85	113	141	from vo)		
Safety laboratory tests 19	X	X		X 	X 	X 	X 	X	$X^{32}$	$X^{32}$	
Anti-drug antibody samples	X	X		X			X	X	X	X	
Injection site inspection 		X		X	X	X	X		X	X	
Telephone call 			X								
Study drug administration 				Daily	dosing		-		X		
Dispense/Return study drug 		X		X	X	X	X		X		
Adverse event assessment 	X	X	X	X	X	X	X	X	X	X	

**Table 3:** Schedule of Assessments (Continued)

Study Period/Procedure	Screening	Study Treatment					EOS Visit	Bridging Visit(s) 31		
Clinic Visit Number	V1	V2	-	V3 	V4	V5	V6 30	V7	+ up to 12 weeks from V6	Treatment Discontinuation Visit
Start of Week X	-8 to -2	0	2	4	8	12	16	20	(up to one year from V6)	

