- 27. Patients/caretakers will return all (the number recorded) used vials to the clinic when they visit, and both clinic-administered study drug as well as outpatient study drug administration will be recorded in a study diary.
- 28. Adverse events will be recorded from the time a patient provides informed consent. AEs reported after dosing on Day 1 will be considered treatment-emergent AEs.
- 29. Patients who are <16 years of age will receive first daily dose of 3.0 mg at V3, at clinic site.
- 30. Study endpoints are analyzed at V6. After completing V6, patient enters a separate extension study (Protocol RM-493-022), does not enter the extension study and returns for the final study Visit 7 in 4 weeks, or completes Bridging Visits for up to one year or until the extension study is initiated.
- 31. Bridging Visits only needed if separate extension study RM-493-022 is not initiated at site at the time of V6.
- 32. Collected prior to study drug administration.
- 33. Although the study procedures and assessments required per protocol are classified as "No or Minimal Risk" (with the exception of may be classified as "Minor Increase over Minimal Risk") according to the 2008 Guidance Document "Ethical Considerations for Clinical Trials on Medicinal Products Conducted with the Pediatric Population," considerations for reducing pain in distress in participants younger than 18 years of age are included in Appendix J.
- 35. Only applicable to SCR1 patients.
- 36. During visit 2 ECG will be collected prior to dosing and ~8 hours post-dose.

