- 9 Early Termination: For those patients who withdraw consent or are withdrawn and not willing to complete the remaining study visits, the early termination visit assessments should be performed, when possible. Final Visit: For patients who complete the study but do not wish to enroll into the future long-term extension study (as noted in Protocol Section 5.5), patients will be required to return for a Final Visit ~ 30 days after the last dose of setmelanotide, for a final follow-up safety assessment. Any ongoing AEs reported at this visit should be monitored as outlined in Protocol Section 7.4. For patients who enroll into the long-term extension study, this visit is not required. Additionally, patients who are not willing to return for the remaining clinic visits/Final Visit, assessments by home health care professionals can be arranged, or at a minimum, patients can be contacted via phone if amenable, to collect self-reported patient data (i.e.: weight, hunger, AEs, etc.).
- 10 [REDACTED]

11 Weight is to be measured at the clinic using the same scale after patients have emptied their bladder and while fasting. Patients are to wear light clothing or underwear, no shoes, and will be weighed at approximately the same time of day. Weight measurements are to be done in triplicate; waist circumference will be single measures.

12 Extra retain samples will consist of 2 serum and 2 plasma (K2EDTA) vacutainer tubes.

13 Study drug is administered by patients/caretakers beginning the morning of Day 1 and for the duration of dosing. Patients/caretakers will draw up and self-administer/administer the drug once on a daily basis in the morning. On days with clinic visits, the patients/caretakers will administer the drug in the clinic in the presence of the clinical staff to assure proper technique. Patients/caretakers will return all used vials to the clinic when they visit (the number recorded) and both clinic administered study drug, as well as outpatient study drug administration will be recorded in a study diary.

14 Injection site evaluations and scoring (by the clinical staff) will include identification and measurement of areas of erythema, edema and induration, as well as the presence of localized pain, tenderness and itching. Additional evaluation data can be collected at any visit where there are injection site reactions even if not a timepoint for formal assessment.

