- # Once a patient's therapeutic dose has been established according to Protocol, no further dose titrations will occur, and patients will transition directly into the 10 week Open Label Active Treatment phase.
- * For patients that reside a considerable distance from the clinic, these visits are optional clinic visits, and may be performed by home health care professionals.

Table 2 Schedule of Assessments: Post-Amendment 9

Study Period/Procedure	Screening	Study Treatment						EOS Visit	Bridging Visit(s) ³¹ + up to 12 weeks from V6 (up to one year from V6)	Treatment Discontinuation Visit
Clinic Visit Number	V1	V2	-	V3 ²⁹	V4	V5	V6 ³⁰	V7		
Start of Week X	-8 to -2	0	2	4	8	12	16	20		
Study Day (\pm 3 days)	-56 to -14	1	15	29	57	85	113	141		
Sponsor review of patient genetics/Genetic Testing ¹	X									
Informed consent/Assent ³³	X									
Inclusion/Exclusion review	X	X								
Medical history review	X									
Physical examination ²	X	X		X	X	X	X	X	X	X
Comprehensive skin exam ³	X						X			X
Fitzpatrick classification scale	X						X	X		X
Hepatic imaging ³⁵	X									
Weight ⁴	X	X		X	X	X	X	X	X	X
Waist circumference ⁵	X	X		X	X	X	X	X	X	X
Height ⁶	X			X	X	X	X	X	X	X
Vitals ⁸	X	X		X	X	X	X	X	X	X
ECG (12-lead) ⁹	X	X ³⁶		X			X		X	X
Pregnancy test ¹⁰	X	X ³²		X	X ³²	X ³²	X ³²		X ³²	X ³²
Daily hunger questionnaires ¹¹	X		Daily ³²							X ³²
Global hunger assessment ¹²		X ³²		X ³²	X ³²	X ³²	X ³²	X	X ³²	X ³²

Study Period/Procedure	Screening	Study Treatment						EOS Visit	Bridging Visit(s) ³¹ + up to 12 weeks from V6 (up to one year from V6)	Treatment Discontinuation Visit
Clinic Visit Number	V1	V2	-	V3 ²⁹	V4	V5	V6 ³⁰	V7		
Start of Week X	-8 to -2	0	2	4	8	12	16	20		
Study Day (± 3 days)	56 to 14	1	15	29	57	85	113	141		
Safety laboratory tests ¹⁹	X	X		X ³²	X ³²	X ³²	X ³²	X	X ³²	X ³²
Anti-drug antibody samples	X	X		X			X	X	X	X
Injection site inspection ²⁴		X		X	X	X	X		X	X
Telephone call ²⁵			X							
Study drug administration ²⁶		Daily dosing							X	
Dispense/Return study drug ²⁷		X		X	X	X	X		X	
Adverse event assessment ²⁸	X	X	X	X	X	X	X	X	X	X

Study Period/Procedure	Screening	Study Treatment						EOS Visit	Bridging Visit(s) ³¹ + up to 12 weeks from V6 (up to one year from V6)	Treatment Discontinuation Visit
Clinic Visit Number	V1	V2	-	V3 ²⁹	V4	V5	V6 ³⁰	V7		
Start of Week X	-8 to -2	0	2	4	8	12	16	20		
Study Day (\pm 3 days)	56 to 14	1	15	29	57	85	113	141		
Concomitant medications review	X	X	X	X	X	X	X	X	X	X

V, Study Visit Number; EOS, End of Study; PK, Pharmacokinetics.

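### Females of child-bearing potential who go from Visit 6 to Visit 7 have no scheduled pregnancy test after the last-dose day, which fits poorly with Protocol 11.15

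*Protocol*

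**What the plan says.** Protocol 11.15 (Contraception) requires of females able to bear children that "a highly reliable form of contraception must be used/practiced throughout the study and for 90 days following the study". For females who reach Tanner Stage 5 or menarche during the study, it says that they are then managed as being of child-bearing potential "for the remainder of the study, with the required pregnancy tests at all visits".

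Protocol Table 3 (Section 10) and SAP Table 2 (Section 1.3.4) schedule pregnancy tests at Screening, Visits 2 to 6, Bridging Visits and the Treatment Discontinuation Visit. In both tables the Visit 7 cell is empty. Footnote 32, attached to the Visit 6 test, reads "Collected prior to study drug administration".

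Protocol 7.1 (Treatment Period) fixes the end of dosing: "At Visit 6, the patient will receive the last setmelanotide injection". Patients who decline the extension study return for Visit 7 four weeks later. According to Table 3, Visit 7 includes a physical examination, safety laboratory tests, anti-drug antibody samples and adverse event assessment. The safety laboratory panel listed in footnote 19 and Protocol 11.18 contains no pregnancy test.

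**The concern.** The text treats pregnancy precautions as continuing past the end of the study, while for one group of patients the schedule stops testing on the last day of dosing. A test taken that morning cannot show a conception in the preceding days. Visit 7 is the only later visit in this study for these patients. It is late enough to show such a conception, and blood is already drawn there.

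The wording for females who mature on study refers to tests at all visits, and Visit 7 is a visit. A site that reads 11.15 literally and a site that follows Table 3 would therefore act differently.

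At stake is whether a pregnancy conceived late in dosing is picked up by a planned procedure, both for the patient's care and for the pregnancy-test listing promised in SAP 4.6.3. No efficacy endpoint, estimate or analysis set is involved.

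**Working it through.** **Step 1. Is the blank cell real?** Each table has ten schedule columns. The pregnancy-test row, with the anti-drug antibody row as a check on column alignment, reads the same in Protocol Table 3 and SAP Table 2:

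| Column | Pregnancy test | Anti-drug antibody |
|---|---|---|
| V1 | yes | yes |
| V2 | yes | yes |
| Day 15 call | – | – |
| V3 | yes | yes |
| V4 | yes | – |
| V5 | yes | – |
| V6 | yes | yes |
| V7 | **blank** | yes |
| Bridging | yes | yes |
| Treatment Discontinuation | yes | yes |

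The antibody row fills its V7 cell, so the columns line up. Two separately printed tables agree, so the blank is not an extraction fault.

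**Step 2. Interval from last test to last visit.** Inputs from Table 3: V6 = Day 113 and V7 = Day 141, each ±3 days.

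- Planned: 141 − 113 = 28 days.
- Shortest: (141 − 3) − (113 + 3) = 22 days.
- Longest: (141 + 3) − (113 − 3) = 34 days.

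**Step 3. Interval from last test to the end of required contraception.** The 90 days run from the end of the study, which for these patients is V7.

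- Planned: 28 + 90 = 118 days.
- With windows: 22 + 90 = 112 to 34 + 90 = 124 days.

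**Step 4. Which conceptions can the V6 test not show?** The documents give no lag from conception to a positive serum test, so the lag L is an assumption, taken over 7 to 21 days. Conceptions from Day 113 − L + 1 to Day 113 are out of reach. Their share of the 16-week (112-day) dosing period is L/112. A V7 test on Day 141 would show conceptions up to Day 141 − L.

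| Assumed lag L | Out of reach at V6 | Share of dosing period | A V7 test shows conceptions up to |
|---|---|---|---|
| 7 days | Day 107–113 | 7/112 = 6.3% | Day 134 |
| 10 days | Day 104–113 | 10/112 = 8.9% | Day 131 |
| 14 days | Day 100–113 | 14/112 = 12.5% | Day 127 |
| 21 days | Day 93–113 | 21/112 = 18.8% | Day 120 |

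In every row the last column is later than Day 113, so a V7 test would cover the whole gap. This holds even at the shortest interval: with 22 days between visits and a 21-day lag, conceptions up to one day after V6 are covered.

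**The case against.** **The group is narrow.** Bridging Visits and the Treatment Discontinuation Visit include a test, and patients who enter RM-493-022 have no Visit 7 here. The gap concerns only females of child-bearing potential who complete Visit 6 and then go to Visit 7. This stands and sets the scope.

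**The expected yield is very small.** The documents give neither a female count nor a pregnancy rate. Assuming 30 to 75 eligible females, 1 to 10% pregnancies per year on contraception and a 14-day gap, the expected number lies between 30 × 0.01 × 14/365 = 0.01 and 75 × 0.10 × 14/365 = 0.3, before restricting to those who attend Visit 7. This stands too.

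**The all-visits wording is ambiguous.** It covers only females who mature on study, and it can be read as meaning the tests that the schedule requires. That weakens it as a contradiction, but an ambiguity between text and table still needs settling.

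**The earlier schedule proves little.** The pregnancy row of SAP Table 1-3 is marked in the Early Termination column. Footnote 9 to that column also says of completers not entering the long-term extension that "patients will be required to return for a Final Visit ~ 30 days after the last dose of setmelanotide". A difference from an earlier design is not in itself an error, so this is context only.

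**Stronger readings that a reader might infer, and why they fail:**

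- *None of the 90-day period is monitored, and a Visit 7 test would cure that.* The 90 days start when the study ends, so Visit 7 precedes them. A test there closes the gap at the end of dosing and leaves the 90 days themselves untested.
- *The study would report no pregnancies.* Tests at Visits 2 to 6 cover most of dosing: (112 − 14)/112 = 87.5% to (112 − 10)/112 = 91.1% at lags of 14 and 10 days.
- *A late conception goes undetected.* Only a scheduled test is missing. The Visit 7 examination, adverse event questioning or an unscheduled test might reveal it.
- *An exposed pregnancy leaves no record, because Protocol Section 12 does not make pregnancy reportable.* The supplied text has gaps around 11.15 to 11.18, so a reporting rule may exist. Congenital anomaly is listed as a serious event (12.1), and related serious events remain reportable after completion of the study (12.2.3).

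**Conclusion.** The point holds within limits. For females of child-bearing potential who go from Visit 6 to Visit 7, the last scheduled pregnancy test precedes the final dose on Day 113, and none follows at the visit 22 to 34 days later. This sits poorly with the contraception period and the all-visits wording in Protocol 11.15, and with the tests kept in the Bridging and Treatment Discontinuation columns. The documents give no reason for the omission.

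The size, which rests wholly on the assumed detection lag, is about 6 to 19% of the dosing period for lags of 7 to 21 days. This is a modest safety follow-up gap with a low likely yield. It is worth closing because closing it is cheap and removes a mismatch between text and table.

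**What to change.** Reconcile Protocol Table 3 and SAP Table 2 with Protocol 11.15 by marking a serum pregnancy test at Visit 7 for females of child-bearing potential, run on the safety-laboratory blood draw already taken there. Settle the all-visits wording in 11.15 at the same time, so that text and tables give one instruction.

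The cost is one extra assay at one visit in a small subset of patients, plus a change to two tables. No extra visit or blood draw is needed.

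Separately, and only as a request, the sponsor should confirm that a procedure exists for reporting pregnancies and their outcomes. The supplied text is too incomplete to say that it is absent.

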## 11.18. Safety Laboratory Tests

Clinical safety laboratory tests will be performed by a central laboratory. Blood and urine samples are to be collected following an 8-hour fast and prior to dosing, according to the SOA (Table 3).

All clinically significant laboratory abnormalities will be followed-up by repeat testing and further investigated per the judgment of the Investigator.

Specific tests are described below.

In certain situations, it may not be feasible to complete all blood draws scheduled for a specific visit (e.g., a younger patient, or difficulty with phlebotomy due to obesity). In this situation, the Investigator may use his/her discretion to determine which laboratory tests are completed. Laboratory tests should be prioritized in the following manner:

1. Safety labs; including hematology, chemistry, and coagulation profile.

3. All other laboratory measures, such as

Any patient who does not complete all blood draws as described in the SOA on two visits should be discussed with the Sponsor.

